Participants were asked to complete Headspace sessions on a daily basis during the 8-week intervention. They were encouraged to first complete the 30-day Foundation Course, which teaches users the basics of mindfulness meditation, then the cancer pack, which was designed specifically for individuals affected by cancer. They also had the option to choose other 10- to 30-day courses that are more condition- or situation-specific, such as "Anxiety," "Stress," "Acceptance," "Relationships," or "Sleep," or single meditation sessions. All Headspace courses teach mindfulness using various basic techniques, including breathing exercises, body scan (to mindfully pay attention to different parts of one's body—one of the most basic exercises in the MBSR program), noting (being aware of any emotions that may be arising at the moment), and visualization (visualizing images such as sun shining on the entire body). The length of the sessions can be set from 10 to 20 minutes. The length was initially set to 10 minutes for all participants. In addition to the daily, progressive audio instruction, there are short (1-2 minutes) lecture videos every several days designed to increase the understanding of mindfulness and to encourage its integration into daily life. Headspace can be set up to send reminders using push notifications, and study staff made phone calls if an intervention participant completed fewer than 3 Headspace sessions in a week.

Wait-list Control Arm. Participants randomized to the waitlist control arm received usual care and were asked not to start any stress reduction programs during the study period. On completion of the 8-week survey, the control participants were provided with a year's subscription to Headspace and instructions on downloading the app.

Outcome Measures

Retention. The retention rate was measured as the proportion of enrolled participants who completed the 8-week survey (the primary outcome time point).

Adherence. The Headspace program automatically collects adherence data, including date, time, length, and name of each session to which participants listened, identified by a study ID. Headspace transferred these adherence data to the researchers monthly during the study. Using these data, we calculated the proportion of days during the 8-week intervention period that each participant used the program for any amount of time.

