Mindfulness. The 24-item Five Facet Mindfulness Questionnaire–Short Form (FFMQ-SF) measures 5 factors representing elements of mindfulness: observing, describing, acting with awareness, nonjudging of inner experience, and nonreactivity to inner experience. Higher scores indicate greater mindfulness.

Post-Intervention Interview. We conducted phone interviews with participants after they completed the 8-week intervention period to obtain qualitative feedback regarding the study. Question topics included benefits of using Headspace, things they liked about Headspace or thought could be improved, suggestions for improving the experience of study participants, and experience being in the wait-list control arm.

Data Analyses

Data from patient participants and caregiver participants were analyzed separately. We described baseline distributions between arms. Retention rates were calculated by dividing the number of participants who completed the 8-week surveys by the number of randomized participants. We used the program usage data collected by Headspace to calculate intervention adherence rates—the percent of days within the 8-week intervention period that participants engaged in at least one Headspace session of any length.

To obtain preliminary efficacy results, we performed repeated measures analysis of variance tests comparing change in outcome measures between baseline and 8-week follow-up survey between intervention and control arms using all participants who completed both surveys. Cohen’s d effect size was calculated by taking the difference between group mean change scores and dividing by the pooled standard deviation. All analyses were intent-to-treat. As a pilot study, this randomized clinical trial was not adequately powered to detect statistically significant differences between groups. As such, standardized effect sizes were calculated to demonstrate effects and trends. Effect sizes of approximately 0.2, 0.5,

and 0.8 are generally considered small, medium, and large effects, respectively.

As a supplementary analysis, we conducted dose-response per-protocol analyses, repeating the analysis but stratifying intervention participants by level of adherence to the mindfulness intervention protocol (percent of days during intervention period used Headspace: <50% and $\geq 50\%$) and comparing with the control participants.

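### The only dose-response analysis splits logged percent-of-days use at an unexplained 50%; a continuous-dose model should be added beside the split

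*Combined protocol and SAP*

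**What the plan says.** Outcome Measures, Adherence, describes the data source: "The Headspace program automatically collects adherence data, including date, time, length, and name of each session to which participants listened". From these records, "we calculated the proportion of days during the 8-week intervention period that each participant used the program for any amount of time". Eight weeks is 56 days, so each intervention participant has a value between 0/56 and 56/56.

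Data Analyses then describes the one analysis that relates use to outcome: "As a supplementary analysis, we conducted dose-response per-protocol analyses". It repeats the repeated measures analysis of variance, "stratifying intervention participants by level of adherence to the mindfulness intervention protocol". The lower level is defined by "percent of days during intervention period used Headspace: <50" percent and the upper level is everything from 50% up. Each level is analysed by repeating the main comparison "and comparing with the control participants".

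Two other statements in Data Analyses bear on precision. "Data from patient participants and caregiver participants were analyzed separately", so each stratum is formed within a smaller group than the whole trial. The plan also says that "this randomized clinical trial was not adequately powered to detect statistically significant differences between groups", and reports standardised effect sizes for that reason.

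The text gives no reason for 50%. The Intervention section asks for daily sessions and triggers a staff call below 3 sessions in a week; neither equals the cut.

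**The concern.** An analysis called dose-response asks whether change rises with use. The split gives 0 days and 27 days of use the same dose, and gives 27 and 28 days different doses. Two bins cannot show whether a gradient is straight, flattens or has a threshold. If the relation is roughly linear, they also estimate its strength less precisely than the full scale does.

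The numbers are likely to be small, since each stratum is part of one arm and patients and caregivers are analysed apart. If few people fall on one side of 50%, the effect size for that side will be very imprecise. At stake is the pilot's only evidence on whether more use goes with more benefit, which a later trial might use to set an adherence target. The finer data are already held.

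**Working it through.** The documents state no sample size, alpha, adherence distribution or share of participants above 50%, so there is no figure of the plan's own to reproduce. Everything below is assumption-based and is shown as a range.

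**Inputs from the plan:** dose X = percent of days used, in steps of 1/56; cut at 50%; strata each compared with control.

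**Assumed:** change is linear in X; X follows one of several Beta shapes on 0-100%; for the three-group calculation, 1:1 allocation and control dose 0.

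**1. Gradient within the intervention arm.** With D = 1 if X is at least 50% and 0 otherwise, loss = 1 - corr(X, D)². For uniform use:
- var(X) = 1/12 and var(D) = 0.5 × 0.5 = 0.25
- cov(X, D) = 0.25 × (0.75 - 0.25) = 0.125
- corr² = 0.125² / (0.25/12) = 0.015625 / 0.020833 = 0.75, so the loss is 25%.

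**2. The comparison as planned (control, below 50%, 50% or more).** Loss = within-group sum of squares of dose / total sum of squares. For uniform use:
- overall mean dose = 0.5 × 0.5 = 0.25; mean square = 0.5 × 1/3 = 0.16667
- total variance = 0.16667 - 0.0625 = 0.10417
- within-group variance: 0 in controls and 0.5²/12 = 0.02083 in each stratum; averaged over everyone, 0.5 × 0.02083 = 0.01042
- loss = 0.01042 / 0.10417 = 10%.

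**3. Other shapes (simulated).**

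| Assumed adherence | Share at or above 50% | Loss within arm | Loss, three groups |
|---|---|---|---|
| Beta(0.3,0.3), strongly U-shaped | 50% | 14% | – |
| Beta(0.5,0.5), U-shaped | 50% | 19% | 9.5% |
| Beta(1,1), uniform | 50% | 25% | 10% |
| Beta(2,2), humped | 50% | 30% | 8.5% |
| Beta(1,2) | 25% | 33% | 16.7% |
| Beta(2,1) | 75% | 33% | 6.7% |
| Beta(1,3) | 13% | 45-46% | 25% |
| Beta(2,5) | 11% | 53-55% | – |
| Beta(5,2) | 89% | 55-57% | 5% |

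A dash means that no figure is given here. Where two values are shown, they differ by whether X is rounded to whole days. The ranges are 14-57% within the arm and 5-25% for three groups. The three-group loss is smaller because much of the spread in dose lies between controls and users, and that survives the split.

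**4. Sample-size equivalent.** The number needed for the same precision rises by 1/(1 - loss): 1/0.86 = 1.16 at 14%, 1/0.75 = 1.33 at 25%, 1/0.43 = 2.33 at 57%.

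**5. Dependence on shape.** Power of the slope test against high versus low within the arm, assuming 30 intervention completers, correlation 0.4 and two-sided 5%:

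| Adherence | True relation | Slope | Split |
|---|---|---|---|
| Uniform | linear | 62% | 48% |
| Uniform | step at 50% | 48% | 62% |
| Beta(1,3) | linear | 60% | 34% |
| Beta(1,3) | step at 50% | 36% | 57% |

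The slope wins when the relation is linear and loses when it is a step at the cut. Even under linearity the gain can be small: with 20 completers and correlation 0.3, about 5 points for uniform use (25% against 20%) and about 3 points for Beta(0.3,0.3).

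**The case against.** The analysis is supplementary, in a pilot that says openly that it is underpowered and reads its results as effect sizes. That power statement concerns differences between arms, not a gradient. An adherence threshold is a usual device in a per-protocol analysis, and two groups against control are easy to read. The planned comparison includes controls, so the within-arm loss overstates what that comparison gives up. The slope is favoured only by assuming linearity. Use is a behaviour after randomisation and is partly shaped by staff calls to low users, so a sharper slope is a more precise association, not a more valid one. The text also reports a finished trial, so a slope added now would be post hoc.

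Most of this stands. It limits the severity and rules out two stronger readings that a reader might infer. The first is that the plan is known to discard some fixed large share, such as 25-45%. That range arises only under particular assumed distributions and only for the within-arm gradient. The second is that a continuous analysis is always better, which the step scenario contradicts.

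What the objection does not answer is the question specific to a dose-response analysis: whether, among users, more use goes with more change. The contrast between users and controls is already estimated by the main analysis. For the gradient itself the within-arm loss is the relevant one, and it affects the width of an interval as much as the power of a test.

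**Conclusion.** The concern holds as a modest, inexpensive improvement. A near-continuous logged dose is reduced to two levels at an unexplained cut, and no full-scale analysis is described. The gradient among users is therefore less precise than it need be if roughly linear, and its shape is hidden whatever it is. Under linearity the loss is about 14-57% within the intervention arm, depending on the assumed adherence distribution (25% if uniform). It is about 5-25% for the planned three-group comparison, with 1:1 allocation and control dose 0 also assumed. The documents cannot narrow either range. The primary between-arm comparison is unaffected.

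**What to change.** Keep the table of both strata against control, state the number in each stratum, and give the reason for 50%. Add, separately for patients and caregivers, a regression among intervention completers of the 8-week score on percent of days used, adjusted for the baseline score. Report the slope per 10 percentage points with its 95% CI, and a scatterplot with a smooth to check for non-linearity. Base any statement about a gradient among users on this model. Label it a non-randomised, exploratory association, and post hoc if it is added after the data have been seen.

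The cost is a few sentences and one regression per outcome in each of the two populations, on data already collected. The drawbacks should be stated with the result: the slope assumes approximate linearity, it is less efficient than the split if the true relation is a step near 50%, a smooth through few points is only a rough check, and self-selection into higher use remains.
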